4.4.3 Other Secondary Endpoints (Magnetic Resonance Imaging)

After baseline, MRI assessments are taken at Years 1, 2, 3, 4, and 5 and at early termination. As the ISP is the main focus for this primary analysis, postbaseline MRI assessments will be presented only in a data listing and not summarized or analyzed at this stage. These postbaseline MRI assessments may be summarized or analyzed in a future analysis when more mature OOE data are available. The postbaseline MRI assessments are as follows:

- T2 lesion volume
- Number of new and/or enlarging T2 lesions since previous MRI
- Number of Gd-enhancing lesions
- Change from baseline in percent brain volume
- Change from baseline in cortical grey matter volume
- Change from baseline in white matter volume
- Unenhancing T1 lesion volume
- Number of Gd-enhancing lesions evolving to black holes since previous MRI
- Number of new T1 hypo-intense (unenhancing) lesions since previous MRI

4.4.4 Exploratory Immunology Endpoints

Between-group comparisons of the exploratory immunology endpoints described below require comparison of Groups A1 and A2, A1 and B, A1 and A2, and A and B. As noted in Section 4.4.2.2 above, the first three of these four comparisons should be interpreted with some caution, since patients were not assigned to Groups A1 and A2 randomly (patients were randomized to Group A or Group B, and within Group A were non-randomly assigned to Group A1 or A2, based on seasonality considerations).

4.4.4.1 Overall Antibody Response to 23-PPV Vaccine

The following analyses will be considered exploratory and may be undertaken, depending on data availability at the time of the primary analysis.

Levels of overall antibody response to the 23-PPV vaccine, IgG (using ELISA) and IgM (using ELISA), measured 4 weeks after administration of the 23-PPV vaccine, and 8 weeks after administration of the 23-PPV vaccine (which is 4 weeks after Group A1 patients received the 13-PCV booster) for patients in Groups A1, A2, A (A1 and A2 combined) and B will be summarized descriptively by treatment group using the same summary statistics as presented in Section 4.4.1 for the primary immunology endpoint.

4.4.4.2 Overall Antibody Response to 13-PCV Vaccine

The following analyses will be considered exploratory and may be undertaken, depending on data availability at the time of the primary analysis.

Levels of overall antibody response to the 13-PCV vaccine, IgG (using ELISA) and IgM (using ELISA), measured 8 weeks after administration of the 23-PPV vaccine (which is 4 weeks after Group A1 patients received the 13-PCV booster) for patients in Groups A1, A2, A (A1 and A2 combined), and B will be summarized descriptively by treatment group using the same summary statistics as presented in Section 4.4.1 for the primary immunology endpoint.

4.4.5 Sensitivity Analyses

If there are any reported major protocol deviations relating to, or other issues reported which may affect data quality or analysis interpretability for a specific primary or secondary immunology endpoint, then as sensitivity analyses, the summaries and analyses specified above for that specific endpoint may be repeated excluding those patients with major protocol deviations/other issues.

4.4.6 Subgroup Analyses

No subgroup analysis is currently planned but may be performed if deemed necessary.

4.5 IMMUNOPHENOTYPING ANALYSES

For immunophenotyping analyses, data will be presented for Groups A1 and A2 separately as well as for Group A (Groups A1 and A2 combined) and Group B.

Summaries will be presented separately within the following study periods:

- ISP
- SFU Period after the ISP (these patients did not enter the OOE)
- OOE
- SFU Period after completing the OOE

The humoral and cellular immunity outcome measures in this study are as follows:

- Flow cytometry, which will include (but is not limited to) the following cells:
 - Total B cells (CD19+)
 - B-cell subsets (e.g., memory B cells, naïve B cells, and plasma cells)
 - Total T cells (CD3+)
 - T helper cells (CD3+ and CD4+)
 - Cytotoxic lymphocyte T (CD3+ and CD8+)
 - Natural killer cells (CD3– and CD16/56+)
- Quantitative Ig:lg levels (including total Ig, IgG, IgG subtypes, IgM, and IgA)

Ocrelizumab—F. Hoffmann-La Roche Ltd
22/Statistical Analysis Plan BN29739

For each flow cytometry parameters, the absolute values and change from baseline (Day 1) will be summarized over time by treatment group. Summary statistics calculated will include mean, median, SD, minimum, and maximum. For CD19 cells, the number and percentage of patients whose CD19 counts have repleted will be presented at each timepoint. Repletion is defined as the CD19-cell count having returned to their baseline value (Day 1) or lower limit of normal (≥ 80 cells/ μL), whichever is lowest. The median CD19-cell count will be displayed graphically over time from the start of study treatment.

For immunoglobulin levels (IgG, IgM, and total Ig), the absolute values and change from baseline will be summarized over time by treatment group. Summary statistics calculated will include mean, median, SD, minimum, and maximum. At each timepoint, the number and percentage of patients with immunoglobulin levels lower than the lower limit of normal will be presented. For each immunoglobulin, the number and percentage of patients with single and replicated laboratory abnormalities will be summarized by treatment group. The mean immunoglobulin levels (IgG, IgM, and total Ig) will be displayed graphically over time from the start of study treatment.

4.6 SAFETY ANALYSES

For safety analyses, data will be presented for Groups A1 and A2 separately as well as for Group A (Groups A1 and A2 combined) and B.

All summaries of safety data will be based on the Safety Population.

4.6.1 Exposure to Study Medication (Ocrelizumab)

4.6.1.1 Exposure to Ocrelizumab during the ISP

Patients will be considered to have received a dose of ocrelizumab treatment if at least one part of one infusion of that dose (i.e., either Day 1 or 15 for dual infusions) was given.

Treatment duration for ocrelizumab-treated patients in the ISP will be calculated as the date of the last recorded observation during the ISP (the date reported on the ISP Completion/Early Discontinuation electronic Case Report Form [eCRF]) minus the date of first dose of ocrelizumab. If protocol requirements are followed exactly, this duration should be 168 days (24 weeks) for patients who do not withdraw/discontinue early.

Exposure to ocrelizumab for patients in Groups A1, A2, and A (Groups A1 and A2 combined) during the ISP will be summarized as follows:

- Dose received on Day 1: number and percentage of patients who received ocrelizumab dose
- Dose received on Day 15: number and percentage of patients who received ocrelizumab dose

- Total cumulative dose of ocrelizumab (mg; Day 1 + Day 15): summary statistics, including mean, median, SD, minimum, and maximum
- Receiving <80% and ≥80% of the planned infusion on Day 1: number and percentage of such patients
- Receiving <80% and ≥80% of the planned infusion on Day 15: number and percentage of such patients
- Pretreatment with steroids on Day 1: number and percentage of patients pretreated on Day 1
- Pretreatment with steroids on Day 15: number and percentage of patients pretreated on Day 15
- Pretreatment with antihistamines on Day 1: number and percentage of patients pretreated on Day 1
- Pretreatment with antihistamines on Day 15: number and percentage of patients pretreated on Day 15

A listing of information relating to exposure to ocrelizumab will be provided.

4.6.1.2 Exposure to Ocrelizumab during the OOE

Patients will be considered to have received a dose of ocrelizumab treatment if at least one part of one infusion of that dose (i.e., either Day 1 or 15 for dual infusions) was given.

The duration of observation for a patient will be calculated as:

(Date of the day prior to the infusion of the last dose in OOE – date of the first infusion in the dose given during the ISP) + 1

Exposure to ocrelizumab for patients in Groups A1, A2, A (Groups A1 and A2 combined), and B during the OOE will be summarized as follows:

- Treatment duration: number and percentage of patients who received 0–23 weeks of treatment, 24–47 weeks of treatment, 48–71 weeks of treatment, 72–95 weeks of treatment, etc.
- Number of ocrelizumab doses: number and percentage of patients receiving 1, 2, 3, 4, etc. doses and summary statistics for the number of ocrelizumab doses (mean, SD, and median)
- Total cumulative dose of ocrelizumab during OOE (mg): summary statistics, including mean, median, SD, minimum, and maximum

A listing showing duration of exposure to ocrelizumab during the ISP and OOE will be provided.

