4.6.2 Adverse Events

Adverse events will be summarized for the ISP and the OOE. Adverse events reported during the SFU Period or B-cell Monitoring Period will be included in the period of previous dose received.

Safety data from this trial will also be included in pooled safety analyses of MS patients treated with ocrelizumab (e.g., malignancy) at interim analyses. These analyses are not described in this document.

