4.6.3.2 Infections and Serious Infections

Infections will be defined from the adverse event data using the MedDRA SOC of “Infections and Infestations”. An infection will be defined as serious if the event is a serious adverse event.

A listing of infections (defined using the MedDRA SOC “Infections and Infestations”) with pathogen information code will be provided. An additional listing will display adverse events from other SOCs with the pathogen information code. Also a listing will display non-serious infections treated with an intravenous anti-infective.

Immunization Study Period

Infections and serious infections will be summarized by SOC and PT. Infections by intensity will be summarized also. If a patient has multiple events, the most extreme intensity will be taken. Infections and serious infections will also be summarized by pathogen type. The number of infections and serious infections per 100 patient-years will be calculated and summarized.

Optional Ocrelizumab Extension

The same summaries will be presented for OOE as for ISP, with the exception of summaries of infections and serious infections by pathogen type.

All Periods

The same summaries will be presented for all study periods as for ISP.

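### The extension exposure formula in SAP 4.6.1.2 includes the immunization-period interval and omits all time after the last extension dose, so it misstates duration whether read as extension-only or cumulative

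*SAP*

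**What the plan says.** SAP 4.6.1.2 deals with ocrelizumab exposure in the OOE. It introduces its only formula with "The duration of observation for a patient will be calculated as". The end point is the "Date of the day prior to the infusion of the last dose in OOE", the start point is the "date of the first infusion in the dose given during the ISP", and 1 is added to the difference.

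The table that follows is for Groups A1, A2, A "and B during the OOE will be summarized as follows". Its treatment-duration row gives the "number and percentage of patients who received 0–23 weeks of treatment, 24–47 weeks of treatment", and so on in 24-week bands. The other rows give the number of doses and the total milligrams in the OOE.

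Three other SAP sections bear on this:

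- 4.6.1.1 defines an ISP treatment duration of its own, from first ocrelizumab dose to last recorded ISP observation. If the protocol is followed exactly, "this duration should be 168 days (24 weeks) for patients who do not withdraw/discontinue early".
- 4.6.2 places late events: "Adverse events reported during the SFU Period or B-cell Monitoring Period will be included in the period of previous dose received".
- 4.6.3.2 plans rates: "The number of infections and serious infections per 100 patient-years will be calculated and summarized". It asks for them in the ISP, the OOE and all periods together.

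**The concern.** A table of extension exposure should start when the extension starts and run to the end of observation in it. This formula does neither. For Group A it starts at the first ISP infusion, 24 weeks before the extension begins. It ends just before the last extension infusion, so the most recent dose contributes no time.

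The timing of the analysis makes this matter. The clinical cutoff falls when all patients have completed or left the ISP (SAP 1 and 2.4), so the last Group A patients to enter the OOE will have little extension time. Each would still be credited with about 24 weeks. The milligrams row in the same table is explicitly limited to the OOE, so adjacent rows would describe different periods. Adverse events after the last OOE dose count towards the OOE, while this formula gives that time no days.

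**Working it through.** **Inputs**

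- Group A first infusion: Day 1 (Protocol 4.3.2.1).
- Group A OOE starts at Dose 2 (Protocol 4.7.10), nominally Day 169, with later doses every 24 weeks, i.e. 168 days (Protocol 4.3.2.1).
- Window for the Day 169 visit: ±4 days (Protocol Appendix 1, Table A).
- Group B receives no ocrelizumab in the ISP (Protocol 4.3.2.1).
- Assumption: the week bands are in completed weeks. The SAP does not say.

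**The plan's own figure.** The ISP duration in SAP 4.6.1.1 is 169 − 1 = 168 days, which agrees with the stated value.

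**The formula as written.** On schedule, the k-th OOE dose falls on Day 1 + 168k. The formula gives

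((1 + 168k − 1) − 1) + 1 = 168k days.

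For k = 1, 2, 3, 4 this is 168, 336, 504 and 672 days (24, 48, 72 and 96 weeks). Follow-up after the last dose does not enter. For k = 1 all 168 days are the ISP interval and none are extension days.

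**The error on each reading.** Let t be the days from the last dose to cutoff, counted inclusively. The cutoff then falls on Day 168k + t.

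- OOE-only exposure from Day 169: (168k + t) − 169 + 1 = 168(k − 1) + t. Formula minus this = 168 − t. That is an overstatement when t < 168 and an understatement when t > 168.
- Cumulative exposure from Day 1: (168k + t) − 1 + 1 = 168k + t. Formula minus this = −t, always a loss.

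| Group A case | t | Formula | OOE-only | Cumulative |
|---|---|---|---|---|
| Dose on Day 169, cutoff Day 175 | 175 − 169 + 1 = 7 | 168 | 7 | 175 |
| Doses on Days 169 and 337, cutoff Day 400 | 400 − 337 + 1 = 64 | 336 | 232 | 400 |

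The OOE-only errors are +161 and +104 days. The cumulative errors are −7 and −64 days.

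**The bands.**

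- OOE-only: on schedule with t < 168, the formula gives exactly 24k weeks and the true value lies between 24(k − 1) and 24k weeks. Every such patient is placed one band too high. In the first case that is 24–47 weeks instead of 0–23; in the second, 48.0 weeks instead of 232/7 = 33.1.
- Cumulative: on exact schedule with t < 168, the true value is 24k + t/7 weeks. The band is then right although the days are short. The band goes wrong once t reaches 168, or when a dose is early. Dose 2 on Day 165 gives 164 days (23.4 weeks) and on Day 173 gives 172 days (24.6 weeks). With cutoff on Day 175 both patients have 175 days (25.0 weeks) of cumulative exposure, yet they fall in different bands.

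**Group B.** There is no ISP ocrelizumab infusion, so the start date does not exist and the formula cannot be evaluated, although the table includes Group B.

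**The case against.** The best defence is that a cumulative duration was meant. The formula is labelled as a duration of observation, the treatment-duration row has no formula of its own, and the closing listing in 4.6.1.2 covers both ISP and OOE. On that reading, counting the ISP interval is correct, and this part of the defence stands. It does not rescue the formula: the lead-in to the table limits it to the OOE, and all time since the last dose is still lost.

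Three stronger readings are tempting, and the documents do not support them.

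- A reader might infer a plain loss of exposure. If t averages 84 days (assumed) and all of about 67 Group A patients enter the OOE, the cumulative reading loses 67 × 84/365.25 = 15.4 patient-years. On the OOE-only reading the same t gives an overstatement of 168 − 84 = 84 days per patient, so the sign reverses. Entry to the OOE is also optional and subject to re-treatment criteria, and the documents give no distribution of t.
- A reader might infer that the OOE infection rates will be wrong. SAP 4.6.3.2 names no denominator. It asks for the same rates in the ISP, where Group B has no ocrelizumab exposure, so an ocrelizumab duration cannot be the denominator throughout. The incidence rates in 4.6.2.1 divide by number of patients and are unaffected.
- A reader might infer that the ISP time is reported twice. SAP 4.6.1.1 defines that duration but does not list it among its summaries.

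It is also fair to say that the table is descriptive, and that SAP 4.4.3 calls the ISP the main focus of this analysis.

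**Conclusion.** The formula is wrong as written for a table of extension exposure, and neither reading makes it right. For Group A on schedule it returns 168 days per OOE dose regardless of follow-up. The error is 168 − t days if OOE-only exposure is meant, and −t days if cumulative exposure is meant. The OOE-only error is largest for patients just after a dose, and a cutoff tied to the end of the ISP will include recent entrants. It turns into an understatement only beyond 168 days since the last dose, for example while infusions are suspended but the patient stays on the OOE schedule, as Protocol 4.1.4 allows in pregnancy.

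The figures rest on nominal visit days and the chosen cutoff days; real values will vary with visit windows and delays. An effect on rates per 100 patient-years is possible but not established. The primary endpoint and the other immunology results are untouched. The point deserves correction because it is a definite error in a safety exposure table, but it goes no further than that.

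**What to change.** In SAP 4.6.1.2:

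1. Define OOE treatment duration as (earlier of the clinical cutoff date and the last recorded OOE observation) − (date of first OOE infusion) + 1. Use it for the week bands, and say that they are completed weeks.
2. Report cumulative exposure from first ocrelizumab infusion as a separate, labelled row. On schedule the parts add up without overlap: 168 ISP days plus (C − 169 + 1) OOE days equals C, for a last counted day C.
3. For OOE rates per 100 patient-years, name a separate denominator in 4.6.3.2: observation time from first OOE infusion to the earlier of the clinical cutoff and the end of the follow-up whose events 4.6.2 attributes to the OOE, including safety follow-up after the OOE. Stopping at the end of the OOE would leave follow-up events in the numerator with no matching time.

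Starting at the first OOE infusion also makes the duration computable for Group B. The cost is a few sentences of SAP text, the corrected duration variable, one added row and a named denominator, all from dates already collected.

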4.6.2 Adverse Events

Adverse events will be summarized for the ISP and the OOE. Adverse events reported during the SFU Period or B-cell Monitoring Period will be included in the period of previous dose received.

Safety data from this trial will also be included in pooled safety analyses of MS patients treated with ocrelizumab (e.g., malignancy) at interim analyses. These analyses are not described in this document.

4.6.2.1 Adverse Events during the ISP

Adverse events will be defined as all adverse events, except non-serious MS relapses, but including infusion-related reactions (IRRs) and serious MS relapses. Therefore, those adverse events recorded on the “adverse event” and “infusion-related reaction (IRR)” CRF pages will be included.

For each adverse event recorded, the term entered by the investigator describing the event (the “reported term”) will be assigned a standardized term (the “preferred term”) based on the MedDRA WHO dictionary of terms. All analyses of adverse event data will be performed using the PTs unless otherwise specified.

All adverse events will be mapped to PTs and superclass terms and included in a data listing (a separate listing showing relapse information will also be presented). For all summary tables, the adverse events will be sorted by SOC (in decreasing order of overall incidence) and then by PT (in decreasing order of overall incidence). An adverse event profile summary table will be presented to provide an overview of adverse events reported in the ISP. Additionally, the most frequent adverse events ($\geq 5\%$ in any treatment group) will be presented by PT.

Summaries of adverse events will be generated by summarizing the incidence of treatment-emergent adverse events only. Treatment-emergent events are defined as those adverse events with observed or imputed onset date on or after the start date of study treatment (ocrelizumab or any vaccinations). Only where the most extreme intensity is greater than the initial intensity will events with an onset date prior to the start of study treatment (and with an end date on or after the start of study treatment) be considered treatment-emergent. An adverse event with a completely missing, non-imputed start date will be assumed to be treatment-emergent unless the adverse event has a complete non-imputed end date that is prior to start of study treatment.

Adverse events will be assigned to a dose if the adverse event onset date is on or after the date of the first infusion of that dose but before the first infusion of the next treatment dose. Adverse events that start prior to the first dose and worsen during treatment (i.e., treatment-emergent) will be assigned to the first treatment dose.

For each treatment group, the incidence count for each adverse event PT will be defined as the number of patients reporting at least 1 treatment-emergent occurrence of the event. The incidence rate will be calculated as the incidence count divided by the total number of patients in the population. Each table will also present the overall number of patients experiencing at least 1 adverse event and the total number of adverse events reported (multiple occurrences of the same adverse event in one patient will be counted only once at the most extreme intensity). For adverse events leading to death, the most extreme intensity will be overwritten by Grade 5 (death).

Serious adverse events will be defined as all serious adverse events, which includes serious MS relapses and serious IRRs. Serious adverse events will be summarized for each treatment group by SOC and PT, and presented in a data listing. Additionally, the most frequent serious adverse events ($\geq 1\%$) will be presented by PT for each treatment group. A separate listing with relapses considered as serious adverse events will be presented. Related adverse events and serious adverse events will be summarized by SOC and PT for each treatment group and separately for adverse events related to (or suspected to be related to) treatment with each of the following:

- Ocrelizumab
- Methylprednisolone
- KLH
- Tetanus and diphtheria vaccine
- Tetanus, diphtheria, and pertussis vaccine
- 23-PPV
- 13-PCV
- Influenza vaccine

Concomitant treatments for adverse events (excluding IRRs and MS relapses) will be summarized by class and PT. Also concomitant treatments starting during the ISP or during the SFU Period following the ISP will be summarized by class and PT.

Adverse events and serious adverse events will be summarized by intensity (most extreme intensity) and overall, by SOC and PT. Additionally, adverse events of intensity grades 3, 4, or 5 (most extreme intensity) will be summarized by intensity and overall, by SOC and PT.

All patient deaths during the study (all study periods) will be included in a data listing.

A patient may experience an adverse event that leads to the discontinuation of their study treatment. Discontinuation of study treatment for an adverse event may not necessarily lead to discontinuation from the study because patients can enter the SFU Periods. Only adverse events that led to the discontinuation of study treatment are of interest. Patients who withdraw early from the study because of adverse events will be

Ocrelizumab—F. Hoffmann-La Roche Ltd
26/Statistical Analysis Plan BN29739

Clinical Study Report: ocrelizumab - F. Hoffmann-La Roche Ltd
Protocol BN29739 Report Number 1079337

summarized under disposition. The number of patients who experienced an adverse event that led to discontinuation of study treatment will be summarized by SOC and PT for each treatment group. A listing will be presented showing all adverse events which led to discontinuation of study treatment.

The number of patients who experienced an adverse event that led to modification or interruption of study drug will be summarized by SOC and PT for each treatment group.

A glossary of superclass terms, PTs and verbatim terms for adverse events will be provided. Also a glossary of superclass terms and PTs for adverse events baskets will be provided.

To comply with the reporting requirements of www.clinicaltrials.gov, the following two tabular summaries will be provided for the ISP. For the two summaries below, unlike all other adverse event summaries in this study, multiple occurrences of the same adverse event in an individual are counted separately:

- Non-serious adverse events reported in $\geq 5\%$ of patients in any treatment group will be summarized by SOC and PT. Non-serious relapses will be excluded here. Within each treatment group, the number and percentage of patients reporting such adverse events, and the number and percentage of events reported, will be presented.
- Serious adverse events will be summarized by SOC and PT. Within each treatment group, the number and percentage of patients reporting serious adverse events, and the number and percentage of serious adverse events reported, will be presented. Further, the total number of serious adverse events in each treatment group that were treatment-related, fatal, and treatment-related and fatal will be presented.

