Approximately 30–35 centers will participate in the study in the United States/North America. This study consists of up to five study periods:

- Screening Period
- Immunization Study Period

Group A: Immunization Study Period and OCR treatment starts at Day 1/Week 1. Patients will receive 300 mg of open-label OCR on Day/Week 1 (Dose 1 Infusion 1) and Day 15/Week 2 (Dose 1 Infusion 2). Patients in Group A will be split and be assigned to either Group A1 (booster 13-PCV) or Group A2 (influenza vaccine). At Day 85/Week 12 patients will start to receive immunizations and undergo post-immunization assessments. For all patients in Group A, the Immunization Study Period will end on Day 169/Week 24.

Group B: Patients will not receive OCR. At Day 1/Week 1, patients will start to receive immunizations and undergo post-immunization assessments. For Group B, the Immunization Study Period will end at Day 84/Week 12.

The timing of immunizations and post-baseline assessments are detailed in [Appendix 1](#).

[figure not shown]
- Optional OCR Extension (OOE) Period:
 - **Groups A1 and A2:** Patients who complete the 24-week immunization study period will have the option for retreatment with a single infusion of 600 mg OCR (Dose 2) at Day 169/Week 24 and subsequent single infusions (600 mg OCR) at intervals of 24 weeks provided that he or she meets the OOE retreatment criteria and chooses to receive retreatment.
 - **Group B:** Patients who complete the 12-week immunization study period will have the option to receive OCR in the OOE; the first dose will be administered as two single infusions of 300 mg, on Day 84/Week 12 (Dose 1 Infusion 1) and Day 98/Week 14 (Dose 1 Infusion 2), and subsequent doses will be administered as single 600 mg infusions (Dose 2, Dose 3, etc.) at intervals of 24 weeks provided that he or she meets the OOE retreatment criteria and chooses to receive retreatment. Group B patients who do not qualify for and/or do not choose treatment with OCR at Week 12 will complete the study at Week 12 and will **not** enter safety follow-up.

Please note that the OOE will continue with all patients who are able to receive OCR as per local guidelines, or unless the Sponsor decides to terminate the OCR program for MS; however, the OOE will not exceed 4 years after the last patient last visit in the Immunization Study Period. *At the end of the OOE, patients may choose to continue on commercially available OCR.*

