4.4.2.5 Seasonal Influenza Vaccine

The influenza vaccine is indicated for immunization against influenza caused by the influenza strains included in the vaccine. The inactivated (or recombinant) vaccine has

been chosen for this study to assess antibody production for a commonly used clinically relevant antigen.

Group A2 patients can receive the influenza vaccine at any time between Day 85/Week 12 and Day 140/Week 20.

Group B patients will receive the influenza vaccine as an IM injection in the deltoid muscle at any time between Day 1/Week 1 and Day 84/Week 12. If a patient needs to receive the influenza vaccine after Week 12, the optional OCR infusion must be delayed.

Group A1 patients can receive the influenza vaccine at any time at the discretion of the investigator.

Refer to the label for dosing and administration guidance.

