- 26 Influenza vaccine for Group B: Influenza can be administered between Weeks 1 and 12. For patients who need to receive the influenza vaccine after Week 12, the OCR infusion must be delayed. Post-vaccine assessments must be done after 4 weeks. For patients in Group B who are due to receive the influenza vaccine during their country-specific influenza vaccine blackout period, administration of the vaccine should be given prior to the start of this blackout period
- 27 M=Sample to be taken prior to immunization on days when vaccines are administered. On infusion visits, all urine and blood samples should be collected prior to the infusion of methylprednisolone. At other times, samples may be taken at any time during the visit.
- 28 TT-containing adsorbed vaccine refers to the combined tetanus and diphtheria (DT/Td) or tetanus, diphtheria, and acellular pertussis (DTaP/Tdap) vaccines.

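### ISP adverse event tables set crude proportions side by side over unequal observation times (about 168 versus 83 days, more where follow-up events are added), and Group B has no stated ISP person-time and no usable OOE duration formula

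*SAP*

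**What the plan says.** **Measure.** For the ISP tables, SAP 4.6.2.1 states: "The incidence rate will be calculated as the incidence count divided by the total number of patients in the population". The all-cause AE, serious AE, intensity and Grade 3–5 tables use this basis, and SAP 4.6 shows A1, A2, A and B together. Treatment-emergent time starts with the first ocrelizumab infusion or vaccination, which is Day 1 in both groups.

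**Period length.** Protocol 3.1: "For all patients in Group A, the Immunization Study Period will end on Day 169/Week 24" and "For Group B, the Immunization Study Period will end at Day 84/Week 12".

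**Follow-up events.** SAP 4.6.2: "Adverse events reported during the SFU Period or B-cell Monitoring Period will be included in the period of previous dose received". Protocol 3.1 and 4.7.4 set follow-up at 48 weeks after the last infusion. Under Protocol 3.1 and 4.7.7, Group B patients who never receive ocrelizumab do not enter it.

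**Boundary between periods.** SAP 4.6.2.1 assigns an event to a dose if it starts on or after that dose's first infusion "but before the first infusion of the next treatment dose". Protocol 4.7.10 starts the OOE at Dose 2 in Group A and at the first two 300 mg infusions in Group B.

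**Person-time.** SAP 4.6.3.2 plans infections and serious infections per 100 patient-years. The only ISP duration rule, in SAP 4.6.1.1, covers ocrelizumab-treated patients.

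**OOE duration.** The formula in SAP 4.6.1.2 starts at the first infusion of the dose given in the ISP and ends the day before the last OOE dose. The same section lists Group B among the groups to be summarized, although Protocol 4.3.2.1 gives Group B no ocrelizumab in the ISP.

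**The concern.** A percentage of patients with an event grows with the time observed. When A and B stand in adjacent columns, a reader cannot tell an ocrelizumab effect from longer observation. The extra time in Group A is the 12 weeks between the first infusion and the first vaccine. The rule on follow-up events lengthens the window further, and only in Group A. The listing of frequent events, with its cut-off of 5% in any treatment group, is exposed in the same way.

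The infection rates would correct for time, but their Group B denominator is left to the programmer. The OOE formula is a separate drafting fault: it returns nothing for Group B and mixes ISP time into the figure for Group A.

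**Working it through.** **1. ISP length.** The rule in SAP 4.6.1.1 is last ISP date minus first-dose date.
- Group A: 169 − 1 = 168 days, which reproduces the SAP's own figure of 168 days (24 weeks).
- Group B, same rule: 84 − 1 = 83 days.
- Ratio: 168/83 = 2.02. With the ±4-day visit windows it runs from 164/87 = 1.89 to 172/79 = 2.18.

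**2. Effect on a crude proportion when the true hazards are equal.** With a constant hazard (assumption), pA = 1 − (1 − pB)^(168/83). If only half of the hazard is time-related (assumption), the exponent is 0.5 + 0.5 × 2.02 = 1.51.

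| Group B | Group A, all time-related | Group A, half time-related |
|---|---|---|
| 10% | 19.2% | 14.7% |
| 30% | 51.4% | 41.7% |

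A term at 3% in Group B would read 6.0% in Group A and so cross the 5% cut-off on time alone. If events follow only the vaccinations that both groups receive, there is no shift.

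**3. Follow-up events counted in the ISP.** Take a Group A patient with a last infusion on Day 15, no OOE and complete follow-up.
- End of follow-up: Day 15 + 48 × 7 = Day 351.
- Time from Day 1: 351 − 1 = 350 days, and 350/83 = 4.2.

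Only data available at the clinical cutoff enter the analysis, and the number of such patients is not given.

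**4. Time after first vaccination.** Group A: 169 − 85 = 84 days. Group B: 84 − 1 = 83 days. A nearly equal common window therefore exists.

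**5. What patient-year rates would do.** Take about 67 and 33 patients (100 at 2:1), nominal windows and no dropout.
- Group A: 67 × 168/365.25 = 30.8 patient-years.
- Group B: 33 × 83/365.25 = 7.5 patient-years.
- Equal constant hazards give equal rates.
- If events follow vaccinations and 10% of each group has one, A is 6.7/30.8 = 22 and B is 3.3/7.5 = 44 per 100 patient-years. The ratio is 83/168 = 0.49, so the rates err in the opposite direction.
- One event in Group B is 1/7.5 = 13 per 100 patient-years, exact 95% CI 0.3 to 74.

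**6. OOE formula: (day before last OOE dose − first infusion of ISP dose) + 1.**
- Group A, one OOE dose on Day 169: (168 − 1) + 1 = 168 days, all of it ISP time.
- Group A, two OOE doses (Days 169 and 337): (336 − 1) + 1 = 336 days, of which 168 are ISP time.
- Group B: no start date exists, so no value.

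The formula is labelled as duration of observation, while the table reports treatment duration in 24-week bands. No sentence links the two.

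**The case against.** The strongest defence is that little depends on these tables. The safety objective in Protocol 2.3 is to collect additional data, no between-group AE difference or interval is planned, the period lengths are stated openly, and a percentage of patients with an event is a legitimate description. Infections, an identified risk, already get a time-based rate. This stands, and it limits the consequence. It does not cure a follow-up rule that works in one group only, a rate without a stated denominator, or a formula with no start date.

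A second defence is that many events cluster around infusions and vaccinations, so time is the wrong divisor. This stands in part. Step 5 shows that patient-year rates alone could make ocrelizumab look safer than it is, so they cannot be the only remedy.

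Several stronger readings are tempting but unsupported:
- A reader might infer that the ISP has no boundary when the first OOE infusion is delayed. SAP 4.6.2.1 read with Protocol 4.7.10 already places that boundary at the first OOE infusion in either group. What is missing is a person-time statement.
- A reader might infer that two-fold is a ceiling. It describes the nominal windows; step 3 exceeds it.
- A reader might infer a Group B ISP running to Day 112, for vaccination on Day 84 plus a 4-week assessment, and hence a ratio of 168/111 = 1.5. Protocol 4.4.2.5 says "If a patient needs to receive the influenza vaccine after Week 12, the optional OCR infusion must be delayed", and footnote 26 of Appendix 1 Table B says "Post-vaccine assessments must be done after 4 weeks". Neither moves the stated end of the ISP, the delay applies only to vaccination after Week 12, and such vaccination would put the assessment later than Day 112. So 1.5 is neither a documented length nor a bound, although some Group B windows may exceed 83 days.
- A reader might infer that the tables prepared "separately for adverse events related to (or suspected to be related to) treatment with each of the following" are untouched where the product is a vaccine. Step 4 supports that only if follow-up events are kept out.

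**Conclusion.** The point holds as a limited fault of definition and presentation. On nominal windows, Group A is observed about twice as long as Group B in the all-cause ISP tables, and a Group A patient who skips the OOE may be counted for up to 350 days. The shift in percentages ranges from none, if events follow shared vaccinations, to nearly two-fold for uncommon events under equal constant hazards. The documents do not show where in that range this trial lies, or how many patients have extended windows. The absence of a stated Group B person-time and the failure of the OOE formula for Group B need no assumption. A reader might infer that the trial's safety conclusions are invalid; the documents do not support that, because the tables are descriptive and no formal AE contrast is planned.

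**What to change.** 1. Amend SAP 4.6.2 so that follow-up events are shown separately from the A-versus-B ISP tables.
2. In SAP 4.6.2.1 keep the proportions and add two summaries of AEs, serious AEs and Grade 3 or higher events: one over a common window from first vaccination (about 84 days in A, 83 in B), and one as rates per 100 patient-years over the ISP. State that the rates assume a roughly constant hazard, that they understate Group A relative to B by up to about half when events follow vaccinations, and that Group B supplies only about 7.5 patient-years.
3. Define ISP person-time for both groups. Start at the first ocrelizumab infusion (A) or first vaccination (B). End the day before the first OOE infusion or, for patients who do not enter the OOE, at ISP completion or discontinuation, or the cutoff. Use it for the infection rates too.
4. In SAP 4.6.1.2 start OOE-only duration at the first OOE infusion in each group. Report cumulative exposure separately, from the first ocrelizumab infusion actually received, and say which of the two feeds the treatment duration categories. State the end date as well: with the present one, a Group A patient with one OOE dose would score (168 − 169) + 1 = 0 OOE days.

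The cost is SAP wording and a few tables; the dates are already collected. The price in interpretation is imprecise Group B rates, so the three displays have to be read together. No clinical procedure changes.
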